Clinical investigation plan

C18-649 (EX-MKTG-99)

A clinical comparison of two daily disposable soft contact lenses

**A clinical evaluation for
CooperVision Inc.**

Principal Investigator
[name]

September 2018

Contents

Document control	3
Study summary	
Section 1. Overview	5
1.1 Background	5
1.2 Personnel	5
1.3 Study objectives	5
1.4 Study design	5
1.5 Statistical considerations	5
1.6 Risk analysis	6
Section 2. Resources	7
2.1 Subject selection	7
2.2 Subject discontinuation	8
2.3 Safety parameters, adverse events and concurrent illnesses	8
2.4 Study termination	9
2.5 Protocol deviations	9
2.6 Study resources	9
2.7 Study control	10
2.8 Documentation	10
2.9 Data collection and analysis	10
2.10 Study completion	11
2.11 Confidentiality	11
2.12 Study monitoring	11
Section 3. Subject management	12
3.1 Visit scheduling	12
3.2 Visit conduct	12
3.3 Monitoring subject compliance	19
3.4 Missing, unused and spurious data	19
Section 4. Study co-ordination	20
4.1 Document processing	20
4.2 Disclosure	20
4.3 Personnel	20

Study summary

This double-masked, randomised, bilateral crossover dispensing study will compare the clinical performance and subjective acceptance of the PremiO 1day and clariti™ 1 day daily disposable soft contact lenses.

Fifty five subjects will be enrolled on this study and will wear each lens type for one week in random sequence. The following will be assessed throughout the study: [REDACTED]
lens fit, [REDACTED] and subjective response.

A study summary is shown in Table 1.

Visit	Procedures
Information presentation Initial visit	
On-line explanation of study procedures and visits.
 
Information and consent forms signed
 
Ocular and contact lens history
 
Medical history
 
[REDACTED]
 
[REDACTED]
 
Application of first lens type
 
[REDACTED]
 
Lens fit [REDACTED] assessment
 
Subjective scores
 
Issue study lenses
 
[REDACTED]
 
[REDACTED]

1-week visit	
Retrieval of unused lenses
 
Subjective scores
 
[REDACTED]
 
[REDACTED]
 
Lens fit [REDACTED] assessment
 
Lenses removed and discarded
 
[REDACTED]
 
Fitting of second lens type
 
[REDACTED]
 
Lens fit [REDACTED] assessment
 
Subjective scores
 
Issue study lenses
 
[REDACTED]
 
[REDACTED]

2-week visit	
Retrieval of unused lenses
 
Subjective scores
 
[REDACTED]
 
[REDACTED]
 
Lens fit [REDACTED] assessment
 
Lenses removed and discarded
 
[REDACTED]
 
Exit statement signed
 
[REDACTED]

Table 1: Study summary.

Section 1. Overview

1.1 **Background**

This project seeks to compare the short-term clinical performance of the PremiO 1day (Menicon Inc), and clariti 1day (CooperVision Inc) daily disposable soft contact lenses.

1.2 **Personnel**

This work will be conducted at Eurolens Research, The University of Manchester under the general direction of [name] PhD MCOptom FAAO FBCLA. The Principal Investigator for the work is [name] PhD MCOptom FAAO FBCLA.

1.3 **Study objectives**

This study aims to compare the short-term clinical performance of the two contact lenses.

1.4 **Study design**

This will be a randomised, double-masked, crossover, bilateral dispensing study, controlled by cross-comparison. Fifty-five subjects will wear each lens brand for approximately one week in random order. Lenses will be worn on a daily wear, daily disposable basis.

1.5 **Study outcomes**

The primary outcome measure of this study will be lens fit. The secondary outcome measure will be vision; and all other measurements will be tertiary outcomes.

1.6 **Statistical considerations and power analysis**

This work is conducted as a non-inferiority study and as such, the null hypothesis to be tested is that the performance of the clariti 1 day lens is inferior to that of the PremiO 1 day lens.

[REDACTED], [REDACTED] and subjective responses will generate data that are likely to be continuous and normally distributed. As such, these will be compared using linear regression models or other parametric methods. [REDACTED]

[REDACTED] Lens fit data are expected to be ordinal data and assessed with non-parametric approaches. Deviations from this statistical plan will be discussed in the final report. Deviations may be necessary due to differences between the actual data distribution compared with the anticipated data distribution.

Power analysis was conducted for the following variables using data from a previous study:

- [REDACTED]
- [REDACTED]
- [REDACTED]
- [REDACTED]
- Vision
- [REDACTED]
- [REDACTED]
- [REDACTED]
- [REDACTED]
- [REDACTED]

[REDACTED]
[REDACTED] A one-sided power analysis for this variable, assuming an alpha of 0.05, a standard deviation of 28.4 units and a meaningful difference of 10 units (on a 100 unit scale) determined that 51 completing subjects would provide 0.80 power. As such, this number of subjects will provide at least 0.80 power for all the variables listed above. To allow for discontinuations, 55 subjects will be recruited.

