3.2 Visit conduct

3.2.1 Pre-enrolment

The subject will receive a study-specific information form outlining the study at least 24 hours before the initial visit.

At a suitable time, each subject will be asked to watch a short on-line information presentation detailing study visits and procedures. They will be asked to complete several multiple-choice questions to gauge their understanding of the study. Upon successful completion of these questions, the subject will be booked to attend the initial visit. Subjects should be asked not to wear their habitual contact lenses on the day of the study visit.

3.2.2 Visit 1

Subjects should attend this visit wearing their spectacles. They will then be required to sign an informed consent form prior to enrolment. A copy of the signed form will be issued to the subject. When the subject has signed the consent form, they are considered to be enrolled on the study.

Subjects will be instructed on the following:

1. Lens handling, application and removal, where necessary.
2. Specific study instructions, such as the importance of not using any other contact lens products.
3. General contact lens information such as the management of red eyes.

The following procedures will be performed (any ocular measurement procedures outlined below will be carried out on each eye):

1. Details of the ocular history and contact lens wearing history of the subject will be noted [REDACTED].
2. Details of general health and medications will be recorded.
3. [REDACTED]
4. [REDACTED]
5. [REDACTED]

6. The investigator will confirm that the subject satisfies all the inclusion and exclusion criteria. Subjects who fail to meet all the criteria at this time will usually be discontinued and replaced. If in the opinion of the investigator, the subject may

be eligible at a later date, the subject may be brought back for up to one repeat visit of this type.

7. The first randomised lens pair [REDACTED] will be fitted and allowed to settle for five minutes. Subjects will apply the study lenses themselves.

8. [REDACTED]

[REDACTED]

[REDACTED]

[REDACTED]

[figure not shown]
[REDACTED]

[REDACTED]

9. [REDACTED]

[REDACTED]

10. The subject will be asked to score the following with reference to appropriate visual analogue scales (0-100) [REDACTED]

11. [REDACTED]

[REDACTED]

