12. Lens fit will be assessed using the following evaluations: horizontal and vertical centration, corneal coverage and movement. Normally, for an acceptable fit, centration and movement will fall within currently accepted clinical criteria [between 1 and +1 on a -2 to +2 grading scale [REDACTED] If the lens is graded as 'unacceptable' (i.e. any of the grades are +2 or -2), the investigator should state why.

13. Subjects will be given a supply of over-labelled contact lenses [REDACTED]. The subject will then be discharged and asked to return for a one-week follow-up visit wearing the study lenses which need to have been worn for at least two hours. Subjects should be asked to wear their lenses for a minimum of eight hours per day and to wear their lenses every day until the next visit unless he/she experiences symptoms such as redness, discomfort etc. on any given day.

[REDACTED]

[REDACTED]

[REDACTED]

[figure not shown]
3.2.3 Visit 2 – follow-up 1

Subjects should attend wearing their study lenses which should have been in situ for at least two hours. Subjects who attend without lenses in situ for at least two hours will usually be rescheduled.

1. Any medical or ocular issues since the last visit will be recorded.
2. [REDACTED]
3. [REDACTED]
4. Retrieval of any unused lenses.
5. [REDACTED]
6. The subject will be asked to score the following with reference to appropriate vertical visual analogue scales (0-100) [REDACTED]

▪ Vision

7. [REDACTED]

The subject will then be discharged and asked to return for a one-week follow-up visit wearing the study lenses which need to have been worn for at least two hours. Subjects should be asked to wear their lenses for a minimum of eight hours per day and to wear their lenses every day until the next visit unless he/she experiences symptoms such as redness, discomfort etc. on any given day.

3.2.4 Visit 3 – follow-up 2

Subjects should attend wearing their study lenses which should have been in situ for at least two hours. Subjects who attend without lenses in situ for at least two hours will usually be rescheduled.

Any medical or ocular issues since the last visit will be recorded.

1. [REDACTED]
2. [REDACTED]
3. Retrieval of any unused lenses.
4. [REDACTED]
5. The subject will be asked to score the following with reference to appropriate vertical visual analogue scales (0-100) [REDACTED]

Three thick black horizontal bars stacked vertically, with a small gap between the top two.

- Vision

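### The non-inferiority null in section 1.6 carries no margin, and the visible text gives the primary outcome, lens fit, no worse direction, comparative summary or margin

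*Combined protocol and SAP*

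**What the plan says.** Section 1.5 names one primary outcome: "The primary outcome measure of this study will be lens fit". Vision is secondary and everything else tertiary.

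Section 1.6 declares non-inferiority and states that "the null hypothesis to be tested is that the performance of the clariti 1 day lens is inferior to that of the PremiO" lens. That sentence contains no redaction, names no outcome and gives no margin. For the primary outcome, the visible analysis text is "Lens fit data are expected to be ordinal data and assessed with non-parametric approaches".

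The sample size paragraph of 1.6 concerns one variable whose name is blacked out. It is one-sided with alpha 0.05 and an SD of 28.4 units, and "a meaningful difference of 10 units (on a 100 unit scale) determined that 51 completing subjects would provide 0.80 power". The 10 units are not called a non-inferiority margin.

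Section 3.2.2 (Visit 1) describes the fit measurement: "Lens fit will be assessed using the following evaluations: horizontal and vertical centration, corneal coverage and movement". The same section says that "any ocular measurement procedures outlined below will be carried out on each eye". Centration and movement are graded from -2 to +2, and a lens with any grade at either end is unacceptable. Table 1 lists "Lens fit [REDACTED] assessment" at dispensing and at follow-up for each lens.

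**The concern.** A non-inferiority null has to say by how much the test lens may be worse. Without that amount, rejecting the null means showing that clariti 1 day is at least as good as PremiO 1 day. That is a different and harder claim, and equal lenses would nearly always fail it. The stated null therefore disagrees with the declared aim and with any non-inferiority reading of the plan's own power calculation.

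For lens fit the gap is wider. An ordinary non-parametric comparison asks whether grades differ. It does not ask whether one lens is worse by more than a tolerated amount, and a non-significant result would not show non-inferiority. Because grades at both ends are unacceptable, a comparison of signed grades also has no direction that means worse. At stake is whether the report can support a non-inferiority statement on the outcome that the plan calls primary.

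**Working it through.** **1. The plan's own figure.** Inputs from 1.6: one-sided alpha 0.05, SD 28.4, difference 10, power 0.80, 51 completers. Assumption: 28.4 is the SD of within-subject differences (the text does not say).

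- Normal formula: n = (28.4 × (1.645 + 0.842) / 10)² = 49.9.
- Paired t test (noncentral t), margin 10, true difference 0: power 0.798 at n = 51 and 0.805 at n = 52.

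The stated 51 is reproduced to within rounding. If 28.4 were instead the SD of a single score, with correlation r between a subject's two scores, the SD of differences would be 28.4 × √(2(1 − r)). The normal formula then gives 100, 75, 50 or 25 subjects for r = 0, 0.25, 0.5 or 0.75. The stated number fits the paired-difference reading, or r near 0.5.

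**2. What the null as written would do.** With no margin, the boundary of the null is a difference of 0. If the true difference is 0, the chance of rejection is alpha, 0.05, whatever the sample size. With the boundary at −10 units, the same 51 completers give 0.798.

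The arithmetic depends only on the 10-unit distance between the null boundary and the assumed truth. A one-sided superiority test with clariti truly 10 units better would give the same n. The number alone therefore cannot show which hypothesis was meant. Given the declared aim, 10 units has to be the margin, and the null should say so.

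**3. Why 10 units cannot serve lens fit.** The visible fit grades span 4 units, from -2 to +2, and the scale for corneal coverage is not visible. A 10-unit margin has no meaning there.

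Direction fails too. Suppose, hypothetically, that every grade for one lens is 0, while for the other half are -2 and half are +2. Paired differences are then +2 and −2 in equal number, and a signed-rank comparison shows nothing. Yet every fit of the second lens is unacceptable under 3.2.2.

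**4. How many readings make up fit.** Assuming that the four Visit 1 evaluations are repeated at follow-up (those steps are not visible): 4 evaluations × 2 eyes × 2 assessments per lens = 16 readings per subject per lens. Without coverage, 3 × 2 × 2 = 12 are on the visible scale. The visible text neither selects among these nor combines them.

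**5. Illustration only: what a fit margin might mean with 51 completers.** The summary, margin and discordance rates here are all assumed. Take fit per subject and lens as acceptable or not, compared by a one-sided 0.05 score test for paired proportions.

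- If no subject is discordant, the one-sided 95% bound is z²/(n + z²) = 2.706/53.706 = 0.050, or 5.0 percentage points. A margin at or below that could not be met.
- With equal lenses and a 10-point margin, exact power is:

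| Discordant subjects | Power |
|---|---|
| 5% | 0.81 |
| 10% | 0.63 |
| 20% | 0.43 |

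**The case against.** The strongest reply is redaction. Text immediately before the lens-fit sentence in 1.6, most of the list of powered variables, and part of the grading bracket in 3.2.2 are blacked out. A fit summary, margin or rule could be there. This stands, so a reader should not infer that the plan has no fit margin; only the visible text can be judged. It does not rescue the null sentence, which is complete and would need aligning with any margin stated elsewhere.

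A second reply is that, for the powered variable, the repair is one of wording, because 10 units already works as a margin. That also stands. A reader might infer that the sample size is wrong; the reproduction in step 1 does not support that.

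A third temptation is to argue that the fit reading, visit and margin could be chosen once the data are seen, because 1.6 says "Deviations may be necessary due to differences between the actual data distribution compared with the anticipated data distribution". The documents do not support this. The sentence concerns the distribution of the data, and so the choice of method. Section 1.6 also commits to discussing deviations in the final report, and section 2.7 masks subjects and investigators.

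Finally, the acceptable/unacceptable example sets aside the ordinal analysis that the protocol expects, and its inputs are not the trial's. It shows that the margin matters. It does not show that this trial is underpowered for fit.

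**Conclusion.** The point holds with medium confidence and should be fixed. The firm part is that the unredacted null has no margin and, read literally, gives equal lenses about a 5% chance of success, against 0.798 when 10 units is the margin. The 0.798 assumes a true difference of 0 and that 28.4 is the SD of paired differences.

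The conditional part is that the visible text does not say what lens-fit result would show non-inferiority, and the 10-unit figure cannot be carried over to it. This depends on what the redacted text in 1.6 and 3.2.2 contains. It would go too far to say that no fit result could ever establish non-inferiority under the full plan.

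**What to change.** Amend section 1.6 before unmasking.

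1. Reword the null as inferior by at least the non-inferiority margin. Confirm that 10 units is that margin for the powered 0-100 variable, and that 28.4 is the SD of paired differences.
2. For lens fit, confirm, or add if redacted text does not already do so, one per-subject summary with a clear worse direction. An example is all grades within the protocol's own acceptable range. State how evaluations and eyes combine, which visit counts, and the margin on that scale.
3. Conclude non-inferiority only if the one-sided 95% confidence bound for the paired difference excludes the margin. State that a non-significant difference test is not evidence of non-inferiority.

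This is a short rewrite and needs no new data. The real cost is that the sponsor must commit to a fit margin in advance, and 51 completers may give it less than 0.80 power. If the redacted text already holds a fit summary, margin and rule, only the null sentence needs aligning.

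### Does naming linear regression for a crossover measured on both eyes undermine the planned 0.80 power or the 5% error rate?

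*Combined protocol and SAP*

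**What the plan says.** Section 1.4 describes a randomised, double-masked, bilateral crossover in which every subject wears both lenses for about a week each. Section 1.6 frames it as non-inferiority of clariti 1 day to PremiO 1 day. For subjective responses and two blacked-out outcome classes it says that "these will be compared using linear regression models or other parametric methods"; more blacked-out text comes straight after. Lens fit, the primary outcome (section 1.5), is assigned to non-parametric methods instead.

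The power statement in section 1.6 reads "A one-sided power analysis for this variable, assuming an alpha of 0.05", with "a standard deviation of 28.4 units" and a meaningful difference of 10 on a 100-unit scale, and concludes that "51 completing subjects would provide 0.80 power". Enrolment is 55. The visible text does not say whether 28.4 is the SD of a within-subject difference or of a single-lens score.

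Section 3.2.2 (Visit 1) states that "any ocular measurement procedures outlined below will be carried out on each eye" and that "Subjects should attend this visit wearing their spectacles". For Visits 2 and 3 (sections 3.2.3 and 3.2.4) the instruction is "Subjects should attend wearing their study lenses which should have been in situ for at least two hours".

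**The concern.** Ordinary linear regression assumes independent observations. Here each subject supplies two periods and, for ocular measures, two eyes in each. Three things could go wrong if the sentence were applied literally with lens as the only term.

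- **Subject ignored.** The standard error would be that of two independent groups, and the within-subject efficiency behind the sample size would be lost.
- **Eyes counted as independent.** The standard error would be too small and false non-inferiority claims too frequent.
- **Period ignored.** The two periods do not begin alike. Subjects arrive at Visit 1 in spectacles, but at Visit 2 they have worn the first lens for at least two hours, and the second lens is fitted at that same visit. A period shift would add noise, and some bias if dropout left the sequences unequal.

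At stake are the 0.80 power and the 5% one-sided error rate.

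**Working it through.** **Inputs from section 1.6:** one-sided α = 0.05 (z = 1.645), power 0.80 (z = 0.842), SD 28.4, difference 10, n = 51. The documents give no correlations and no period effect, so every value of these below is an assumption.

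**1. Reproduce the 51.**
- Within-subject: n = [28.4 × (1.645 + 0.842) / 10]² = 49.87, so 50 by z. The noncentral t gives 52.
- Power at 51 is 0.808 by z and 0.798 by t. A crossover model with period fitted (n − 2 degrees of freedom) also gives 0.798. If all 55 complete, the paired t gives 0.825.
- Independent groups: 2 × 49.87 = 99.7, so 100 per lens. Paired two-sided: 64 by z.
- If 28.4 were a single-lens SD, n = 2(1 − ρ) × 49.87, which is 100, 75, 50 and 25 at ρ = 0, 0.25, 0.5 and 0.75. So 51 would need ρ near 0.5.

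On either reading the planners assumed a within-subject contrast.

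**2. Ignore subject (28.4 taken as the SD of differences).** The mean difference still varies with its true SE, 28.4/√51 = 3.98, because the data remain paired. Only the estimated SE changes, by a factor 1/√(1 − ρ). The critical value becomes 1.645/√(1 − ρ), and power is Φ(10/3.98 − critical value), with 10/3.98 = 2.51.

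| ρ (assumed) | critical value | actual one-sided α | power |
|---|---|---|---|
| 0.3 | 1.97 | 0.025 | 0.71 |
| 0.5 | 2.33 | 0.010 | 0.57 |
| 0.7 | 3.00 | 0.001 | 0.31 |

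The loss of power is large, but the error rate falls. This mistake cannot produce extra false non-inferiority claims.

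**3. Count 102 eye-level differences as independent.** The ratio of naive to true SE is 1/√(1 + k), where k is the between-eye correlation of the differences. Actual α = 1 − Φ(1.645/√(1 + k)): 0.090, 0.110 and 0.116 at k = 0.5, 0.8 and 0.9, with a ceiling of 0.122 at k = 1. If subject were ignored as well, the ratio would be 1/√[(1 − ρ)(1 + k)]. Over ρ = 0.25–0.75 and k = 0.5–0.9, α then runs from 0.004 to 0.084, so the two errors partly offset and must not be added.

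Which outcomes does this reach? The only unredacted outcome in the regression sentence is subjective response. Sections 3.2.2 to 3.2.4 have the subject score this on 0–100 scales, with no per-eye score described. Vision appears at Visits 2 and 3 as one of these scales. Lens fit is graded on each eye but is sent to non-parametric methods.

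**4. Omit period, sequences balanced.** A 10-unit period effect raises the estimated SD to √(28.4² + 10²) = 30.1. The critical value is 1.645 × 30.1/28.4 = 1.74 and power is Φ(2.51 − 1.74) = 0.78, against 0.81 by z with no period effect. Actual α is 0.041, so error is not inflated. At 5 and 15 units, power is 0.80 and 0.74. If dropout left 27 and 24 subjects in the two sequences, a 10-unit period effect would bias the lens difference by 10 × 3/51 = 0.6 units.

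**The case for a change.** The strongest reply is that permitting a sound analysis is not the same as specifying one. A paired and an unpaired comparison both satisfy the sentence, and a non-inferiority trial ought to fix the choice before unmasking. The same openness affects the primary outcome: a signed-rank test on one value per subject and a rank-sum test on all eyes are both non-parametric. The two-eye point may also reach a continuous measure, since inclusion criterion 7 in section 2.1.3 requires logMAR acuity in each eye and vision is the secondary outcome. Finally, section 3.4 allows partial datasets; a mixed model would use them and a paired test would drop them.

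Much of this stands as a description of what the visible text omits. It does not show that the plan leads to a wrong analysis. Blacked-out text sits exactly where model terms could be stated, so their absence cannot be established. Whether acuity is analysed, and per eye, is not visible. Section 3.4 requires the number of subjects in each analysis to be reported, so handling of partial data would be open to inspection. On period, Table 1 has a blacked-out step between removing the first lens and fitting the second, all subjects already wear lenses habitually (section 2.1.3), and each follow-up assessment comes after about a week of wear.

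**Conclusion.** The concern does not call for a change. It is right that 51 rests on within-subject variation, and that the visible text states no model terms, no rule for combining eyes and no definition of the 28.4. But a linear regression may contain subject and period terms, and the alternative that section 1.6 allows covers a paired t test or a mixed model. Sections 1.4 and 2.7 present the trial as a crossover controlled by cross-comparison, and the sample size itself points to a paired analysis. Carried out that way, 51 completers give 0.798, and 52 reach 0.80 by t.

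The possible losses depend on departing from that reading. Ignoring subject gives power 0.71 to 0.31 over assumed correlations 0.3 to 0.7, in the conservative direction. Counting eyes as independent gives error of 0.09 to 0.12, but only for a per-eye continuous outcome, and none is visibly covered by the sentence. Omitting period costs about 3 points of power at an assumed 10-unit effect with balanced sequences. For lens fit, a paired subject-level test is likewise the natural choice in this design. This is a gap in written detail that analysts would fill sensibly; it would be worth asking the sponsor what 28.4 denotes, but the conclusion does not depend on the answer.

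### Does deriving 51 completers from a 100-unit score leave the ordinal primary outcome, lens fit, without a power basis?

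*Combined protocol and SAP*

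**What the plan says.** Section 1.5: "The primary outcome measure of this study will be lens fit". Section 1.6 sets a non-inferiority framework, with clariti 1 day tested against PremiO 1 day, and adds: "Lens fit data are expected to be ordinal data and assessed with non-parametric approaches".

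The same section then reports the sizing: "Power analysis was conducted for the following variables using data from a previous study". Ten bullets follow. Nine are blacked out and the readable one is vision. The line after the list is also redacted, as is the text just before the calculation. The readable calculation is one-sided, "assuming an alpha of 0.05, a standard deviation of 28.4 units and a meaningful difference of 10 units (on a 100 unit scale"). It gives 51 completers for 0.80 power, and the plan concludes that "this number of subjects will provide at least 0.80 power for all the variables listed above". Recruitment is set at 55 to cover discontinuations.

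Section 3.2.2 (Visit 1), item 12, describes the primary outcome: "Lens fit will be assessed using the following evaluations: horizontal and vertical centration, corneal coverage and movement". Centration and movement are graded "on a -2 to +2 grading scale", and a fit is unacceptable if "any of the grades are +2 or -2". Part of this item is redacted too.

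**The concern.** A trial is normally sized on its primary outcome. Here the primary outcome is a short ordinal grade, while the number of subjects comes from a 100-unit scale, which in the readable text is used only for subjective visual analogue scores. On a quick reading, the study appears to be powered for a lower-ranked outcome and not for the one that carries the non-inferiority claim.

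Two further features add to the doubt. Lens fit has four parts, so a power of 0.80 per variable need not be 0.80 for lens fit as a whole. And both ends of the -2 to +2 scale are bad, so a one-sided comparison needs a definition of worse fit. If lens fit had no margin and no power calculation, a non-inferiority result on it would be hard to interpret, and nobody could say whether 51 completers were ample or too few.

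**Working it through.** **1. Inputs (section 1.6).** One-sided alpha 0.05, SD 28.4, difference 10, target power 0.80, 51 completers, 55 recruited. The design is a two-period crossover (section 1.4). The plan does not say whether 28.4 is the SD of within-subject differences; that reading is tested here.

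**2. Reproducing 51.**

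- Paired normal formula: n = (SD × (z0.95 + z0.80) / difference)² = (28.4 × (1.645 + 0.842) / 10)² = 49.9, so 50.
- Exact paired t test (noncentral t): power 0.798 at 51, 0.805 at 52, 0.825 at 55.
- Readings that do not fit: two-sided paired, 64; parallel groups, 100 per arm.
- If 28.4 were a single-period SD, the same n would need a within-subject correlation of 0.5; a correlation of 0.3 gives 70 and 0.7 gives 30.

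The stated 51 lies between the normal and exact answers and is reproduced to within one subject. Recruitment also agrees: 55 - 51 = 4, and 4/55 = 7.3%, a plausible allowance.

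**3. Is the sizing variable lens fit?** Almost certainly not. Two grades on a -2 to +2 scale differ by at most 4 in either direction, so the SD of their difference cannot exceed about 4. An SD of 28.4 is impossible there. This remains an inference: the variable's name is redacted, and the readable text ties the scale to centration and movement, not clearly to corneal coverage.

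**4. What the list implies.** In a paired comparison with no true difference, power at fixed n depends only on the ratio of margin to SD of the differences. For the sizing variable that ratio is 10/28.4 = 0.352. A listed variable with a larger ratio has more power. Stating that 51 suffices for the whole list therefore amounts to saying that the 100-unit variable is the most demanding. That is a legitimate way to choose n, and it covers lens fit if lens fit is listed.

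**5. Can lens-fit power be checked?** No. Its margin and SD are not readable. For orientation only, with assumed ratios, true difference 0, one-sided 0.05, n = 51 and a paired t test:

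| Assumed margin/SD | Power |
|---|---|
| 0.20 | 0.41 |
| 0.25 | 0.55 |
| 0.30 | 0.68 |
| 0.352 | 0.798 |
| 0.40 | 0.88 |
| 0.50 | 0.97 |

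A rank test with an assumed efficiency of 0.955 changes little (0.792 at a ratio of 0.352). The table straddles 0.80, and nothing in the documents says which row applies. It also treats worse fit as a shift in one direction, which is not what a scale that is unacceptable at both ends measures: one lens at -1 and the other at +1 differ by two grades, yet both are acceptable. So the table shows that the answer depends on inputs not visible here. It is not an estimate of lens-fit power.

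**The case for a change.** The strongest case for a change is that some questions remain even if lens fit is on the list. The 0.80 statement applies variable by variable, while lens fit comprises four evaluations, and no readable rule says whether one or all must be non-inferior. The direction of worse is not spelled out for a one-sided test. The one readable powered variable, vision, is also a 0-100 visual analogue item at Visits 2 and 3, which hints that the list may consist of subjective scores. Writing down a margin and a power figure would cost a sentence or two.

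Part of this stands. The public text does not let a reader verify lens-fit power, and asking whether lens fit is on the list is reasonable. The rest does not amount to a defect:

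- The vision item is only suggestive, with nine of ten names hidden.
- Any loss of power from requiring all four evaluations presupposes a success rule that the readable plan does not state.
- Item 12 does give an overall criterion, since any grade at either extreme makes the fit unacceptable, so what counts as poor fit is not wholly undefined.
- A margin, a grade definition or a decision rule could sit in the redacted parts of section 1.6 or of item 12. Text hidden in the public copy cannot be counted as absent from the plan.

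**Conclusion.** No change to the plan follows. The sample-size arithmetic is right for the variable it describes, to within one subject (50 by the normal formula, 52 by the exact t test, 51 stated). This assumes that 28.4 is the SD of within-subject differences. Choosing n from the most demanding of several powered variables is sound, and the 55 recruited would give 0.825 for that variable if all completed.

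What remains is a limit of the public copy: it does not show whether lens fit is among the nine redacted variables, or with what margin. If it is, the plan already asserts at least 0.80 power for it. If it is not, the 0.80 statement simply does not reach lens fit and should be read as confined to the variables listed. Either answer leaves the ordinal endpoint, the non-parametric analysis and the recruitment of 55 as they are. The possible effect on lens-fit power has no determinable size or direction, because every lens-fit input would have to be assumed. This is a low-priority query to the sponsor.
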